4. CLINICAL TRIAL/INVESTIGATION FLOW AND FOLLOW-UP SCHEDULE

4.1 *Number of Subjects to be Registered*

Approximately 2600 subjects will be registered in ABSORB IV from approximately 140 sites in the United States and outside the United States. The enrollment/registration of ABSORB IV will start after the completion of enrollment/registration of the 2000 primary analysis subjects of ABSORB III.

4.2 *ABSORB Physician Training*

[figure not shown]
Investigators that have not participated in previous ABSORB trials or are not commercial users of the Absorb BVS device will participate in the ABSORB IV physician training program. Please refer to **section 4.2** of ABSORB III Protocol ([REDACTED], August 09, 2018) for the detailed information on the didactic training.

4.3 *ABSORB IV Treatment Flow and Lesion Selection*

A maximum of three *de novo* native coronary artery lesions will be treated in a maximum of two epicardial vessels, with a maximum of two lesions per epicardial vessel. If there are two target lesions within the same epicardial vessel, the two target lesions must be at least 15 mm apart. One planned non-target lesion is allowed in ABSORB IV treated with a XIENCE per the IFU. However, in situations where treatment of a target lesion reveals additional lesion(s), the investigator may treat the lesion(s). This is considered an unplanned lesion. If the lesion meets enrollment criteria both before and after pre-dilatation, the lesion must be treated with the assigned device and will be considered to be an unplanned target lesion. If the lesion does not

meet the enrollment criteria (either before or after pre-dilatation), the lesion must be treated with XIENCE. This lesion will be considered as an unplanned non-target lesion.

Figure 4.1 shows the lesion treatment for subjects in ABSORB IV.

Every attempt should be made that the two or three target lesion treatments occur at the same index procedure. However, if a staged procedure becomes necessary (e.g. due to high use of contrast or radiation after treatment of the first lesion), it is strongly recommended that the staged procedure occurs within 2 weeks of the index procedure using the assigned device, but in all cases no more than 35 days from the index procedure. To avoid having to cross a previously implanted study device, it is strongly recommended that the staged lesion(s) be located in a separate epicardial vessel from the lesion(s) previously treated during the first intervention. A maximum of one staged procedure is allowed. Staged procedures must only include target lesions identified at the time of the index procedure.

Prior to treatment with the assigned device (Absorb BVS or XIENCE), vessel sizing by visual estimation must be conducted to appropriately match the device to the size of the vessel. Quantitative methods such as on-line QCA, IVUS or OCT may be used if the site is experienced with these techniques. Specifically, use of pre-PCI and post-PCI IVUS or OCT is strongly

recommended to optimize device sizing results. Details on the vessel sizing methods can be found in **Imaging Guidance Document**.

To exclude enrollment of excessively small vessels, if the operator believes that based on visual angiographic assessments, the distal reference vessel diameter is ≤ 2.75 mm such that the plan is to implant a 2.5 mm device (stent or scaffold) in a target lesion, it is strongly recommended that either on-line QCA or intravascular imaging (ultrasound or optical coherence tomography) is used and demonstrates that the measured distal RVD for this target lesion is ≥ 2.50 mm (by at least one of these imaging modalities). This measurement may be performed before or after pre-dilatation, but before randomization. If the distal RVD measures <2.5 mm, that lesion IS NOT ELIGIBLE for randomization. Such a lesion may be treated as a non-target lesion. **Table 4.1** provides the device sizes, RVD and lesion length for ABSORB IV.

Table 4.1 Absorb BVS and XIENCE Sizes

Device	Lesion and Device Sizes	
	RVD ¹	Lesion Length ¹
Absorb BVS (Target lesion)	RVD ≥ 2.50 mm - ≤ 3.75 mm Scaffold diameter: 2.5, 3.0 and 3.5 mm	Lesion length ≤ 24 mm Scaffold Length ² : 8, 12, 18 and 28 mm ³
XIENCE ⁴ (Target lesion)	RVD ≥ 2.50 mm - ≤ 3.75 mm Stent diameter: 2.5, 2.75, 3.0, 3.25 3.5, 4.0 mm	Lesion length ≤ 24 mm Stent Length: 8, 12, 15, 18, 23 and 28 mm ³

¹ Reference vessel diameter (RVD) and lesion length based on visual estimation

² Both the 8 mm and 12 mm lengths will be available for the 2.5/3.0 diameter Absorb BVS. Only the 12 mm length will be available for the 3.5 mm diameter.

³ For target lesion, planned overlapping is not allowed (i.e., the lesion must be eligible for treatment with a single stent). However, bailout overlapping is allowed if required.

⁴ XIENCE V, XIENCE Prime, XIENCE Xpedition, XIENCE Alpine, XIENCE Pro, and XIENCE Pro^X will be used in this study.

The commercially approved CE marked 23mm Absorb BVS device will not be used in this study.

It is highly recommended a minimum of 2 mm (by visual estimation) of minimally diseased tissue be covered by the device at both the proximal and distal edges.

Planned overlap of the target lesion is not allowed. Overlap in the case of bailout is allowed. Please refer to **Section 7.3.5** for details regarding bailout.

4.4 Measures Taken to Avoid and Minimize Bias

In ABSORB IV there will be several measures taken to avoid and minimize bias such as randomization and blinding. This process is detailed in the following sections.

4.4.1 Randomization

Stratified Randomization:

[Redacted text block]

[Redacted text block]

[REDACTED]

Timing of Randomization:

[REDACTED]

[REDACTED]

[REDACTED]

4.4.2 Blinding

[REDACTED]

[REDACTED]

[REDACTED]

[REDACTED]

[REDACTED]

[REDACTED]

4.5 Early Termination of the Clinical Trial

Please refer to **section 4.6** of ABSORB III Protocol ([REDACTED], August 09, 2018) for the relevant information about trial early termination.

5. ENDPOINTS

5.1 Primary Endpoints

TLF through 30-day, tested for non-inferiority against the control

- This analysis will consist of ~2600 subjects in ABSORB IV.
- TLF is defined as composite of Cardiac Death, Myocardial Infarction (per protocol-defined MI definition, Appendix II) attributable to Target Vessel (TV-MI), or Ischemia-Driven Target Lesion Revascularization (ID-TLR).

5.2 ABSORB IV Major Secondary Endpoint

- **TLF through 1-year, tested for non-inferiority against the control**
- **ABSORB IV Angina Powered Secondary Endpoint:** The percentage of patients who experienced angina within 1 year, tested first for non-inferiority with reflex to superiority against the control.
 - Angina is defined as any angina or angina equivalent symptoms determined by the physician and/or research coordinator after interview of the patient, and as adjudicated by a clinical events committee (CEC).

- This analysis will exclude angina or angina equivalent symptoms that occurred following the index procedure through hospital discharge or 7 days, whichever occurs first.
- This analysis will consist of ~2600 subjects in ABSORB IV.

5.3 *Additional Secondary Endpoint(s)*

In ABSORB IV the following clinical secondary endpoints will be analyzed for all the ~2600 subjects.

- **Acute Success:** (Combined Clinical/Angiographic Endpoint)
 - Device success (Lesion level analysis)
 - Procedural success (Subject level analysis)
- **Clinical Endpoint** in hospital and at each follow-up point (30, 90, 180, 270 days; 1, 2, 3, 4, 5 years).
 - **Component**
 - Death (Cardiac, Vascular, Non-cardiovascular)
 - Myocardial Infarction
 - Attributable to target vessel (TV-MI)
 - Not attributable to target vessel (NTV-MI)
 - Target Lesion Revascularization (TLR)
 - Ischemia driven TLR (ID-TLR)
 - Non ID TLR (NID-TLR)
 - Target Vessel Revascularization (TVR,)
 - ID TVR
 - Non ID TVR
 - All coronary revascularization
 - **Composite Endpoints**
 - Death/All MI
 - Cardiac Death/All MI

- Cardiac Death/TV-MI/ID-TLR (TLF)
- Cardiac Death/All MI/ID-TLR (MACE)
- Cardiac Death/All MI/ID-TLR/ID-TVR, non TL (Target Vessel Failure, TVF)
- Death/All MI/All revascularization
- **Scaffold-Thrombosis / Stent Thrombosis (per ARC definition)**
 - Timing (acute, sub-acute, late and very late)
 - Evidence (Definite and Probable)
- Rehospitalization
 - Coronary artery disease related
 - Cardiovascular, non-CAD related
 - Non-cardiovascular related
- Repeat coronary arteriography
- TLF through 5 years based on 4600 subjects (2000 primary analysis subjects of ABSORB III and 2600 subjects of ABSORB IV)

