Primary Endpoint	
TLF through 30-day, tested for non-inferiority of Absorb BVS to XIENCE.
 
• This analysis will consist of ~2600 subjects in ABSORB IV.
Powered Secondary Endpoints	
1. TLF through 1 year, tested for non-inferiority of Absorb BVS to XIENCE.2. Angina Powered Secondary Endpoint: The percentage of patients who experienced angina within 1 year, tested first for non-inferiority of Absorb BVS to XIENCE with reflex testing to superiority.
• Angina is defined as any angina or angina equivalent symptoms determined by the physician and/or research coordinator after interview of the patient, and as adjudicated by a clinical events committee (CEC).• This analysis will exclude angina or angina equivalent symptoms that occurred following the index procedure through hospital discharge or 7 days, whichever occurs first.
○ For subjects who receive a planned staged procedure to treat one or more target lesions, the analysis will exclude angina or angina equivalent symptoms that occurred following the original index procedure through hospital discharge or 7 days after the final procedure, whichever occurs first.

	These analysis will consist of ~2600 subjects in ABSORB IV
Patient Reported Outcome (PRO) Informational Endpoints	
Patient-reported outcomes (PRO) are informational endpoints to assess Health-Related Quality of Life. PRO assessments will be conducted at baseline, 1 and 6 months, and at 1, 3 and 5 years. The following questionnaires will be used in this study:
 
 • Seattle Angina Questionnaire-7 (SAQ-7) to assess disease-specific Quality of Life • EuroQoL 5D (EQ-5D) survey to assess overall health status 
(Note: PRO endpoints will be evaluated in the ~2600 subjects of ABSORB IV)
 
The PROs will be analyzed to evaluate the relationship between quality of life and cardiovascular events that occurred post-PCI and to substantiate the clinical impact of the angina events identified in the trial.

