7.4 Post-procedure

7.4.1 Post-procedure Information to be Recorded

The following information needs to be obtained between 12 hours following the index procedure and hospital discharge (in-hospital stay is considered to be a maximum of 7 days following the index procedure).

Between 12 hours post-procedure and discharge

- Date of discharge
- Antiplatelet medications
- Chronic concomitant medications
- Adverse Events, if any

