7.4.2 Post-procedure Laboratory and Clinical Tests

The following laboratory assessments need to be obtained between post-index procedure and hospital discharge. Hospital discharge cannot occur prior to 16 hours to ensure complete post-procedure cardiac enzyme collection.

IMPORTANT: These tests must be performed whether or not they are considered part of the Investigator's standard of clinical practice.

Post-procedure and discharge

- A 12-lead ECG must be obtained within 24 hours post procedure.

- Both Creatine kinase (CK) and Creatine kinase myocardial-band isoenzyme (CK-MB) must be obtained for ALL subjects as it will be used for cardiac assessment of subjects post-index procedure
 - First post-procedure CK and CK-MB draw at 6 to 12 hours post-procedure.
 - Second post-procedure CK and CK-MB draw at 18-24 hours post-procedure, or at the time of discharge as long as discharge is at or after 16 hours post-procedure**.
 - If either of the post-procedure CK-MB levels are $\geq 5x$ ULN, serial CK and CK-MB levels must be drawn until they are falling.

** For subjects discharged prior to 16 hours, the subject will have to return to the enrolling institution for their second biomarker draw.

Alternatively, a visiting nurse may be sent to the patient's home to collect the blood sample. CK and CK-MB levels are required at all time points. Troponins are required pre-procedure and from the arterial sheath prior to first balloon inflation during the procedure in patients with acute coronary syndromes. All troponin, CK and CK-MB levels collected at any time points pre-procedure, during the procedure and post-procedure, should also be documented in the electronic case report forms.

For subjects having staged procedures, the post-procedure cardiac enzyme and 12-lead ECG assessment for the original index procedure must be repeated following the staged procedure in the same manner as done for the original index procedure.

7.4.3 Assessment of perception bias.

Patients' perception as to whether they received the control or test device may affect the rate of angina. As described in section 4.5.2, comprehensive efforts will be undertaken to maintain patient blinding. Nonetheless, for a variety of reasons patients may develop a belief as to which device they received, even if the blind is maintained.

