10.3.2 Powered Secondary Endpoints

Powered Secondary Endpoint 1: TLF through 1 year

TLF at 1-year will be tested for non-inferiority. This analysis will consist of ~2600 subjects in ABSORB IV.

The hypothesis test is designed to show non-inferiority of Absorb BVS to XIENCE for the TLF at 1 year with a one-sided alpha of 0.025. [REDACTED]

[REDACTED]

[REDACTED]

Power Secondary Endpoint 2: Angina through 1 year

The Angina Powered Secondary Endpoint of percentage of patients who had angina within 1 year (excluding an angina blanking period of the index hospitalization or the first 7 days post PCI, whichever occurs first) will be tested for non-inferiority with reflex testing to superiority. This analysis will consist of ~2600 subjects in ABSORB IV.

The hypothesis test is designed to show non-inferiority of Absorb BVS to XIENCE for angina within 1 year with a one-sided alpha of 0.025. [REDACTED]

[REDACTED]

appropriate. In addition, logistic regression will be performed to determine whether the baseline characteristics exhibit any trends in predicting TLF.

For continuous variables such as age, means, standard deviations, and 95% confidence intervals for the mean will be calculated and p-values may be presented for hypothesis generating purposes. For time-to-event variables, such as time to TLF, survival curves will be constructed using Kaplan-Meier estimates, and log rank test results may be displayed. Unless specified, analyses will be performed with pooled data across all study sites.

For further details refer to the statistical analysis plan (SAP).

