1.3 Study Design

ABSORB IV is a prospective, randomized (1:1, Absorb BVS to XIENCE), single-blind, multi-center study, registering approximately 2600 subjects at approximately 140 sites.

The enrollment of the 2600 subjects in ABSORB IV will start after the enrollment completion of the 2000 primary analysis subjects in ABSORB III.

Table 1 provides the device sizes, the reference vessel diameter (RVD) and lesion length for ABSORB IV.

[&] The term “Absorb BVS” will be used to represent both Absorb[™] BVS and Absorb GT1[™] BVS.

^{*} Commercially approved XIENCE family stent system, inclusive of XIENCE V, XIENCE PRIME, XIENCE Xpedition, XIENCE Alpine, XIENCE Pro (OUS only), and XIENCE Pro^X (OUS only).

Table 1. Absorb BVS and XIENCE Sizes

| Device | Lesion and Device Sizes | |
|--|--|--|
| | RVD ¹ | Lesion Length ¹ |
| Absorb BVS ⁴ (Target lesion) | RVD ≥ 2.50 mm - ≤ 3.75 mm Scaffold diameter: 2.5, 3.0 and 3.5 mm | Lesion length ≤ 24 mm Scaffold Length ² : 8, 12, 18 and 28 mm ³ |
| XIENCE ⁵ (Target lesion) | RVD ≥ 2.50 mm - ≤ 3.75 mm Stent diameter: 2.5, 2.75, 3.0, 3.25, 3.5, 4.0 mm | Lesion length ≤ 24 mm Stent Length: 8, 12, 15, 18, 23 and 28 mm ³ |

¹ Reference vessel diameter (RVD) and lesion length are based on visual estimation.

² Both the 8 mm and 12 mm lengths will be available for the 2.5/3.0 diameter Absorb BVS. Only the 12 mm length will be available for the 3.5 mm diameter. The commercially approved CE marked 23mm Absorb BVS device will not be used in this study.

³ For target lesion, planned overlapping is not allowed (i.e. the lesion must be eligible for treatment with a single stent). However, bailout overlapping is allowed if required.

⁴ Once Absorb GT1™ BVS System is commercially available, it can also be used in the ABSORB IV trial.

⁵ XIENCE V, XIENCE Prime, XIENCE Xpedition, XIENCE Alpine, XIENCE Pro, and XIENCE Pro^X will be used in this study.

All registered subjects in ABSORB IV will receive the following clinical follow-up:

- 30 ± 7 days follow-up telephone contact/office visit
- 90 ± 14 days follow-up telephone contact/office visit
- 180 ± 28 days follow-up telephone contact/office visit
- 270 ± 28 days follow-up telephone contact/office visit
- Annual visits: 1-7 years ± 28 days follow-up telephone contact/office visit

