1.3.2.2 Powered Secondary Endpoint #2: Angina through 1 year

Angina through 1 year will be tested first for non-inferiority of Absorb BVS to XIENCE with reflex testing to superiority.

This analysis will consist of ~2600 subjects in ABSORB IV.

- Angina is defined as any angina or angina equivalent symptoms determined by the physician and/or research coordinator after interview of the patient, and as adjudicated by a clinical events committee (CEC).
- This analysis will exclude angina or angina equivalent symptoms that occurred following the index procedure through hospital discharge or 7 days, whichever occurs first.

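### The early exclusion period for the powered 1-year angina endpoint ends at hospital discharge, so which early symptoms count depends on a post-randomisation event

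*Protocol*

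**What the plan says.** Three places define the same window. ABSORB IV section 5.2 excludes angina or equivalent symptoms "that occurred following the index procedure through hospital discharge or 7 days, whichever occurs first". Section 10.3.2 describes the endpoint as "excluding an angina blanking period of the index hospitalization or the first 7 days post PCI, whichever occurs first". SAP 1.3.2.2 states: "This analysis will exclude angina or angina equivalent symptoms that occurred following the index procedure through hospital discharge or 7 days, whichever occurs first".

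The ABSORB IV Protocol Summary adds a version for staged subjects that the other three places lack. It excludes symptoms that "occurred following the original index procedure through hospital discharge or 7 days after the final procedure, whichever occurs first".

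The visible text limits discharge timing in two ways. Section 7.4.2 says "Hospital discharge cannot occur prior to 16 hours to ensure complete post-procedure cardiac enzyme collection", but the same section also provides: "For subjects discharged prior to 16 hours, the subject will have to return to the enrolling institution for their second biomarker draw". Section 7.4.1 says the "in-hospital stay is considered to be a maximum of 7 days following the index procedure". No discharge criteria and no common discharge day appear.

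The endpoint is the percentage of subjects with any angina within 1 year. It is tested for non-inferiority and then, if that succeeds and the Absorb rate is lower, for superiority (section 10.4.2).

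**The concern.** A subject is randomised during the index procedure and discharged afterwards, so the length of the excluded period is itself an outcome of what happened after randomisation. Two consequences follow from the wording alone:

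- Identical symptoms are classified differently. Angina on day 2 is an endpoint event for a subject discharged on day 1 and is ignored for a subject still in hospital.
- The rule can exempt its own events. Chest pain that delays discharge lengthens the exclusion period that covers it.

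Adjudication by the clinical events committee does not repair this. It decides whether a symptom is angina (sections 7.5 and 9.1), not when counting starts.

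If one arm stayed longer, its angina count would fall without any difference in angina. The documents show ways in which stay could come to depend on the device. CK-MB at or above 5 times the upper limit requires serial draws until it falls, and post-dilatation is strongly recommended for Absorb but left to standard practice for XIENCE. These are possible routes, not evidence of a difference.

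**Working it through.** **The plan's own figure.** SAP 1.5.2.2 gives 1235 per arm, a 7-point margin, one-sided alpha of 2.5% and about 99% power by the Farrington-Manning test. The assumed angina rate is redacted. With equal rates in both arms, the same test gives 99.1% power at 20%, 98.0% at 25% and 97.3% at 27.9%. The stated power is plausible but cannot be confirmed.

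**Inputs for the size of the effect.**

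- 1235 per arm: SAP 1.5.2.2.
- Angina at 30 days of 5.8% (Absorb) and 12.5% (XIENCE): ABSORB IV section 12.2, a non-randomised comparison of site-reported angina.
- 1-year angina rate of 25%: assumption.
- Mean stay half a day longer in the Absorb arm: assumption.
- Timing of early angina: either uniform over 30 days, or a first-week daily rate three times that of the remaining 23 days. Both are assumptions.

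**Formulas.** Standard error of the difference = sqrt(2 × 0.25 × 0.75 / 1235) = 1.74 points. Daily rate = R/30 if uniform, or 3R/(3 × 7 + 23) = 3R/44 if the first week is three times higher. Shift = daily rate × 0.5 day. One-sided false-superiority rate = P(Z > 1.96 − shift/1.74).

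| 30-day rate R | Timing | Points per day | Shift (points) | False superiority |
|---|---|---|---|---|
| 5.8% | uniform | 0.19 | 0.10 | 2.8% |
| 5.8% | first week 3 times | 0.40 | 0.20 | 3.2% |
| 12.5% | uniform | 0.42 | 0.21 | 3.3% |
| 12.5% | first week 3 times | 0.85 | 0.43 | 4.3% |

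False superiority of Absorb requires Absorb events to be hidden, so the 5.8% rows are the relevant ones. The 12.5% rows show what would follow if early angina with Absorb were as frequent as the quoted XIENCE figure.

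All four rows are upper bounds for their assumptions. They treat every hidden episode as a lost endpoint subject, whereas a subject with later countable angina that year is counted anyway.

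**Non-inferiority.** At a true difference of 7 points, shifts of 0.1 and 0.4 points in favour of Absorb raise the one-sided error from 2.5% to 2.8% and 4.1%. If XIENCE stays were the longer ones, the same shifts would lower power from 98.0% to 97.7% and 96.5%. The error at the margin moves about as much as the superiority error, but a shift of 0.1 to 0.4 points is small against a 7-point margin.

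**No difference in stay.** If discharge timing is the same in both arms, the shift is zero.

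**The case against.** The strongest reply is that discharge-dependent counting is harmless when both arms are discharged alike. Both arms have the same post-procedure draws and the same 16-hour text. Appendix III describes discharge before 16 hours as the practice of certain hospitals, which would apply to both arms. Variation between subjects and sites then leaves a 1:1 randomised comparison valid.

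The rule also has a rationale: it separates periprocedural pain in hospital from symptoms after going home, it is capped at 7 days, and it matches ABSORB III (sections 5.2 and 10.3.2 of that part). A fixed 7-day window discards genuine angina after discharge and drops early events from an endpoint first tested for non-inferiority. The section 12.2 rates are site-reported, and the text does not say whether in-hospital symptoms were included. A fixed-window sensitivity analysis may lie in redacted SAP text.

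All of this stands as a limit on size. None of it makes the window independent of discharge.

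Two stronger readings are tempting and are not supported:

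- A reader might infer that staff who know the device decide discharge, so the endpoint is open to deliberate or unconscious bias. The SAP says "ABSORB IV is a prospective, randomized (1:1, Absorb BVS to XIENCE), single-blind, multi-center study", and the implanting operator must know the device. But the visible text does not say who decides discharge, and both blinding sections (Protocol ABSORB IV 4.4.2, SAP 1.6.2) are redacted.
- A reader might triple the 30-day average XIENCE rate (3 × 12.5/30 = 1.25 points per day) and arrive at a shift of about 0.6 points and 5.3% false superiority. That would put 7 × 1.25 = 8.75 of the 12.5 points into the first week, and it applies the control rate to events removed from the Absorb arm.

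**Conclusion.** The point holds as a weakness of definition. The excluded period is set by a post-randomisation event that chest pain can itself prolong, and no visible text corrects for this. It is not a demonstrated bias: that would need a difference in discharge timing between arms, and the documents give no data on one.

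With Absorb stays half a day longer, a 25% angina rate and the 5.8% Absorb figure, one-sided false superiority rises from 2.5% to at most about 2.8% to 3.2%. With the 12.5% figure the bound is 3.3% to 4.3%. A longer stay in the XIENCE arm would work against Absorb instead. The superiority test is the more exposed of the two, and the non-inferiority conclusion is unlikely to turn on shifts of this size.

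This is worth correcting because it is cheap. Making the fixed window the main definition is preferable but more debatable than adding it as a second analysis.

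**What to change.** - In ABSORB IV sections 5.2 and 10.3.2 and SAP 1.3.2.2, pre-specify an analysis with one exclusion period for every subject: through day 7 after the index procedure, which is the plan's own cap, whatever the discharge date. Make it the main definition if possible and a sensitivity analysis at minimum.
- Report the discharge-based version beside it and tabulate length of stay by arm. Discharge date is already recorded (section 7.4.1).
- State one rule for staged subjects and align the Protocol Summary with the other three places.
- Reconcile the two statements in section 7.4.2 about discharge before 16 hours.

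The cost is wording in the protocol and SAP and one further table. Either rule needs symptom onset dates. In the fixed-window analysis, angina between discharge and day 7 no longer counts, and the definition differs from that of ABSORB III. Reporting the discharge-based result alongside keeps both the early post-discharge events and the link to that trial.
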